* Interim phone calls will be given 7 days [+8 days of time window] after each injection (PC1: V01 + 7 days, PC2: V02 + 7 days, Group 2 only], PC4: V04 + 7 days, PC5: V05 + 7 days [Group 2 only], and PC7: V07 + 7 days and approximately 2 months after blood samples (PC3: M3 or M4, PC6: M9 or M10, and PC8: M15 or M16) during the 6-month period after each vaccination with the CYD dengue vaccine.

A full physical and clinical examination will be performed and documented on each vaccination visit (mandatory before vaccination) and at the Investigator's discretion if necessary based on the health status of the subject for ***. Vaccinations and associated or subsequent procedures may be out of the defined time-windows in dengue-immune subjects continuing the study due to the pause of vaccine injections (as per Protocol Amendment 1). the other visits.

11: In female subjects of childbearing potential: result of urine pregnancy test should be confirmed as negative before vaccination.

1 msuch case, 1 unplanned acute blood sample (approximately 3 mL) will be collected for virological confirmation of dengue disease by NS1 (nonstructural protein 1) antigen test (ELISA), and/or WT dengue RT-PCR. Concomitant therapy and ongoing medication will be collected for Days 0-28 after each injection only.

Blood samples planned during vaccination visits will be taken before vaccination.

\$\$: Solicited injection site reactions will be collected for Days 0-7 after each injection. Solicited systemic reactions will be collected for Days 0-14 after each injection. Unsolicited for Days 0-28 after each

injection. Serious adverse events (SAEs) will be reported throughout the study and AEs of special interest (AESIs) will be collected in defined time windows according to the type of AESI (hypersensitivity/allergic reactions serious or not] within 7 days after each CYD dengue vaccine injection, serious viscerotropic disease within 30 days after each CYD dengue vaccine injection, serious neurotropic disease within 30 days after each CYD dengue vaccine injection; serious dengue cases requiring hospitalization [i.e., hospitalized suspected dengue case] will be reported during the entire study).

§§§: Termination record will be checked either during a planned study visit or a phone call.

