- for CYD dengue vaccine immunogenicity assessments by dengue neutralizing Abs (4 mL) before the first vaccination (at D0 in Group 1, and M1 in Group 2), and 28 days after each vaccination with CYD dengue vaccine (M1, M7 and M13 in Group 1, and M2, M8 and M14 in Group 2)
- for HPV immunogenicity assessments by competitive Luminex immunoassay (cLIA) (2 mL) before the first vaccination at D0, and 28 days after each vaccination with Gardasil (M1 and M7)

Additional blood samples may be collected at any time throughout the study period:

• In the event of a hospitalized suspected dengue case, all subjects, whether dengue exposed or not, will be sampled (3 mL approximately), within the first 5 days after (or as soon as possible if not within the 5 days) of fever onset, for virological confirmation by NS1 Ag ELISA, and/or WT dengue RT-PCR

- In the event of SAEs (including serious AEs of special interest [AESIs]) and
- To assess AEs that may be indicative of viscerotropic or neurotropic disease (see Guidelines for Assessing Viscerotropic and Neurotropic AE).

Urine samples

All female subjects of childbearing potential will provide urine samples for urine pregnancy test before each injection.

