5.1.4 Visit Procedures

All information collected during the study visits must be reported into the source documents. Some of the following information will also be recorded in the CRF.

Visit 1 (Day 0): Inclusion, Randomization, and Vaccination

The Investigator or designated study personnel will:

- 2) Give the subject's parent/legally acceptable representative information about the trial, obtain written informed consent (ICF and AF when applicable), and give him/her a signed copy.
- 3) Check inclusion and exclusion criteria for eligibility.
- 4) Obtain significant medical history about the subject and history of dengue infection.
- 5) Collect demographic data.
- 6) Check concomitant medications and record every reportable medication ongoing at the time of vaccination.
- 7) For female subjects of childbearing potential^a, perform a urine pregnancy test.
- 8) Allocate a subject number to the subject.
- 9) Scratch off the randomization list to obtain the group allocation, and sign it.
- 10) Perform a physical examination
- 11) Record the subject's axillary temperature.

^a To be considered of non-child-bearing potential, a female must be pre-menarche, surgically sterile, or using an effective method of contraception or abstinence from at least 4 weeks prior to vaccination and until at least 4 weeks after vaccination.

- 12) Obtain blood sample^a (see Section 7.1 for detailed instructions regarding the handling of blood samples). Blood is to be taken from the limb opposite to the one that will be used for vaccination for sequential injection (Group 2), or from the limb opposite to the one that will be used for CYD dengue vaccine injection for concomitant injection (Group 1).
- 13) Inject the first dose of Gardasil to all subjects (from Groups 1 and 2) and the first dose of the CYD dengue vaccine to subjects randomized into Group 1 (for concomitant vaccination, the injections are made in opposite deltoid).
- 14) Keep the subject under observation for 30 minutes, and record any immediate adverse AE in the source document.
- 15) Record the date of injection(s), the site and side of injection(s) and the route of administration(s), as well as the dose number of the vaccine(s).
- 16) Give the parent/legally acceptable representative a diary card (DC), a thermometer, and a ruler, and go over the instructions for their use.
- 17) Remind the parent/legally acceptable representative to bring back the DC when they return for Visit 2 at a specified date and time.

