5.2.5 Exclusion Criteria

An individual fulfilling *any* of the following criteria is to be excluded from trial enrollment:

- Subject is pregnant, or lactating, or of childbearing potential (to be considered of nonchildbearing potential, a female must be pre-menarche, surgically sterile, or using an effective method of contraception or abstinence from at least 4 weeks prior to the first vaccination and until at least 4 weeks after the last vaccination^a)
- 2) Participation at the time of study enrollment (or in the 4 weeks preceding the first trial vaccination) or planned participation during the present trial period in another clinical trial investigating a vaccine, drug, medical device, or medical procedure
- 3) Planned receipt of any vaccine in the 4 weeks following any trial vaccination
- 4) Previous vaccination against dengue disease with the trial vaccine
- 5) Previous vaccination against HPV disease with either the trial vaccine or another vaccine
- 6) Receipt of immune globulins, blood or blood-derived products in the past 3 months
- 7) Known or suspected congenital or acquired immunodeficiency (including HIV infection with impaired immune function); or receipt of immunosuppressive therapy, such as anti-cancer chemotherapy or radiation therapy, within the preceding 6 months; or long-term systemic corticosteroid therapy (prednisone or equivalent for more than 2 consecutive weeks within the past 3 months)

^a For pre-menarche females, the young female patients will declare by themselves (and/or their parent(s) or other legally acceptable representative) if they have not yet started menstruation. If a young female patient reaches menarche during the study, then she is to be considered as a woman of childbearing potential from that time forward. Examples of effective methods of contraception include oral contraception (pill), intrauterine device, diaphragm or condoms, contraceptive foam or cream, hormonal implants, transdermal patch, or parenteral contraception

- 8) History of HPV infection, confirmed either clinically, serologically, or microbiologically as reported by subject or parent(s) or another legally acceptable representative
- 9) Known systemic hypersensitivity to any of the vaccine components^a, or history of a lifethreatening reaction to the vaccines used in the trial or to a vaccine containing any of the same substances
- 10) Thrombocytopenia, contraindicating intramuscular vaccination

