| Addendum I to Assent and Informed Consent        |   |                         |                         |                        | X (Amdt 1)
(as applicable)  | X (Amdt 1)
(as applicable) |  |  |  |  |
| Inclusion/Exclusion Criteria                     | X   |                         |                         |                        |  |                               |  |  |  |  |
| Significant Medical History                      | X   |                         |                         |                        |  |                               |  |  |  |  |
| History of Dengue Infection/Vaccination          | X   |                         |                         |                        |  |                               |  |  |  |  |
| Demography/Body Stature                          | X   |                         |                         |                        |  |                               |  |  |  |  |
| Physical/Clinical† Examination        | X   | X                       | X                       | X                      | X  | X                             | X                                      | X                                      |  |  |
| Temperature                                      | X   | X (Group 2)             |                         | X                      | X (Group 2)  |                               | X                                      |  |  |  |
| Concomitant Therapy‡                  | X   | X                       | X                       | X                      | X  | X                             | X                                      | X                                      |  |  |
| Urine Pregnancy Test††                | X   | X (Group 2)             |                         | X                      | (Group 2)  |                               | X                                      |  |  |  |
| Randomization                                    | X   |                         |                         |                        |  |                               |  |  |  |  |
| Contraindications                                |   | X (Group 2)             |                         | X                      | X  | X                             | X                                      |  |  |  |

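### Read literally, the pregnancy test before a remaining CYD dose is not required for a girl already post-menarche at entry who reports contraception or abstinence

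*Protocol*

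**What the plan says.** **Who is tested.** Protocol Section 5.1.3 states: "All female subjects of childbearing potential will provide urine samples for urine pregnancy test before each injection". The footnote in the Table of Study Procedures adds: "In female subjects of childbearing potential: result of urine pregnancy test should be confirmed as negative before vaccination". Section 7.1.4 confines the test to the same group and lists V01, V02 (Group 2), V04, V05 (Group 2) and V07. The Visit 5 step in Section 5.1.4 uses the same term. Visit 7 does so by referring back to Visit 4.

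**Who is of childbearing potential.** The Visit 1 test step carries a footnote: "To be considered of non-child-bearing potential, a female must be pre-menarche, surgically sterile, or using an effective method of contraception or abstinence". Its window is "abstinence from at least 4 weeks prior to vaccination and until at least 4 weeks after vaccination". Exclusion criterion 1 in Section 5.2.5 bars females of childbearing potential and exempts the same three categories, with the window stated as "abstinence from at least 4 weeks prior to the first vaccination and until at least 4 weeks after the last vaccination".

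**Change of status.** The footnote to exclusion criterion 1 says: "If a young female patient reaches menarche during the study, then she is to be considered as a woman of childbearing potential". That sentence makes no exception for contraception or abstinence.

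**What stops dosing.** Section 5.2.7.2 makes pregnancy a definitive contraindication and describes it as shown by a positive urine test. Section 5.2.12 rules out further vaccination once a pregnancy is known.

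**The concern.** One definition does two jobs. As an eligibility rule, it is reasonable to admit post-menarche girls only if they use contraception or abstain. As the trigger for a pregnancy test, the same definition removes those girls from testing, although they are the eligible girls at entry in whom a test could be informative.

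At stake is a participant safeguard. CYD is a live attenuated vaccine, and the contraindication for pregnancy is worded around the result of a test. Where the test is not required, dosing rests on what a girl aged 9 to 13 at entry, or her parent, reports. Two sites could act differently, one following the text and the other the apparent intent, and both could believe that they complied.

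**Working it through.** The plan gives no figure to reproduce. The check sets the definition against each place where the test is prescribed.

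**Step 1. Sort girls by the literal text.**

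| Girl | Status under the text | Consequence |
|---|---|---|
| Pre-menarche | Not of childbearing potential | No test; reasonable |
| Surgically sterile | Not of childbearing potential | No test; reasonable |
| Post-menarche at entry, no contraception or abstinence | Of childbearing potential | Excluded by criterion 1 |
| Post-menarche at entry, reports contraception or abstinence around the dose | Not of childbearing potential | Eligible; **test not required** |
| Post-menarche at entry, no longer within the four-week window at a later dose | Of childbearing potential under the Visit 1 footnote | Test required |
| Reaches menarche during the study | Of childbearing potential from then on | Test required; the two footnotes conflict if she also reports contraception or abstinence |

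**Step 2. Visit 1.** Criterion 1 excludes everyone of childbearing potential, and the test applies only to those of childbearing potential. The overlap between eligible and testable girls is therefore empty. A scheduled test with no eligible target indicates faulty wording.

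**Step 3. Remaining doses.** When this protocol version was written, Gardasil dosing was complete and all but 8 subjects, all in Group 2, had received CYD dose 2 (Section 5.1.3). The open injections are dose 3 at V07 in both groups and dose 2 at V05 for those 8. Nowhere in either document is a test expressly ordered for the girl in the fourth row.

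**Step 4. Other checks on contraception.** The eligibility step, "Check inclusion and exclusion criteria for eligibility", is listed at Visit 1, and the SAP Table 3.1 row "Inclusion/Exclusion Criteria" is marked at V01 only. Neither list of contraindications (Sections 5.2.7.1 and 5.2.7.2) mentions contraception or abstinence. Time from the Visit 1 check to each open dose, as planned and if the hold of about 2 months delays the dose in full:

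- Group 1, dose 3: 12 months; 12 + 2 = about 14.
- Group 2, dose 3: 13 months; 13 + 2 = about 15.
- Group 2, dose 2 (the 8 subjects): 7 months; 7 + 2 = about 9.

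These intervals show how old the Visit 1 check would be. They do not measure the gap, which depends on status around each dose.

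**Step 5. Size.** Planned girls: 528 × 2/3 = 352. Number affected at dose 3 = 352 × s × m × r, where s is the share seropositive and consenting to further CYD doses, m the share post-menarche and not sterile at entry, and r the share still reporting contraception or abstinence around the dose. The documents give none of the three, and the Synopsis says that the number of dengue-exposed subjects is not known. The range is therefore 0 to 352, with 352 a ceiling and not an estimate. The V05 part is at most 8 subjects, whose sex and serostatus are not stated.

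**The case against.** The strongest reply is that this is ambiguous wording and not a missing test. Several parts of that stand.

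- **The footnote is marked at Visit 1 only.** The later steps use the term without it, so carrying the contraception limb to V05 and V07 is an inference. The only sentence on how status changes after entry turns on menarche, with no contraception exception. A reader might infer that the protocol expressly exempts these girls at the later doses; it does not. But the matching definition in exclusion criterion 1 is the only other one, and it has the same limb. The menarche sentence does not reach girls already post-menarche at entry.
- **Intent.** A reading that empties the Visit 1 test is unlikely to be what was meant. Tests at every injection visit point to testing all post-menarche girls. That stands, and it is a reason to make the text say so.
- **Status must be established at each dose.** A reader might infer that nobody looks at contraception again after Visit 1. That goes too far: staff cannot apply the test step without first deciding whether the girl is of childbearing potential. What is absent is a separate listed step for it.
- **Other safeguards.** Contraindications are reviewed before dosing at V05 (Group 2) and V07, a physical examination precedes each vaccination, and known pregnancy bars further dosing. These narrow the gap but are not stated to include a pregnancy test for these girls.
- **Site practice.** The Operating Guidelines hold detailed procedures and are not available here, so what sites actually do cannot be inferred.
- **The SAP.** Its footnote repeats the protocol's schedule and feeds no analysis. Rewording it would not change who is tested.

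**Conclusion.** The point holds as a defect in the stated rule and should be fixed. Read literally, a girl post-menarche at entry who reports contraception or abstinence around a dose is not required to have a pregnancy test before a remaining CYD injection. For the later visits the text is at best inconsistent, and the probable intent was to test her.

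The number affected is unknown and may be small or zero. A reader might infer that no girl in the trial is tested, or that pregnant girls will be vaccinated. The documents support neither: girls who reach menarche during the study, and those who fall outside the four-week window, come under the test, and untested does not mean pregnant. Endpoints, analysis sets, power and alpha are unaffected.

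The conclusion assumes that the definition in the Visit 1 footnote and exclusion criterion 1 also governs the term at V05 and V07, and that no document outside the protocol and SAP overrides it.

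**What to change.** Change the protocol only:

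1. For the pregnancy test, define childbearing potential as post-menarche and not surgically sterile, regardless of contraception or abstinence.
2. Keep contraception or abstinence in exclusion criterion 1 as a separate eligibility condition.
3. Require a negative urine test in all such girls before each remaining CYD injection: V07, and V05 for the Group 2 subjects awaiting dose 2.
4. Use the same term in the Synopsis, the Table of Study Procedures, and Sections 5.1.3, 5.1.4 and 7.1.4.

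The cost is one reworded definition and a few extra urine tests of a kind already scheduled. Matching the footnote in SAP Table 3.1 is optional, for consistency only.

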Dengue unexposed subjects (seronegative, See Section 9.1.1.1 for definition) at baseline will not receive further dengue vaccine injection. If they consent to continue their participation in the study, they will be contacted by phone call for a safety follow-up 6 months after the last injection. They will not attend any further study visits, except the unscheduled visit and/or the next schedule visit planned to sign the AF and ICF during which they will be proposed to have a blood sample for the assessment of HPV antibodies after the 2 doses of Gardasil.

For dengue exposed subjects who consent to continue in the study and receive the CYD dengue vaccine injection(s), procedures will be as follows:

Vaccinations

Subject will receive a total of 5 injections, i.e., 3 doses of the CYD dengue vaccine and 2 doses of Gardasil administered either concomitantly (Group 1) or sequentially (Group 2), according to the following schedule:

- **Group 1**: Gardasil and the CYD dengue vaccine (concomitantly) at Day (D)0 and Month (M)6, and CYD dengue vaccine (alone) at M12
- **Group 2**: Gardasil (alone) at D0 and M6, and the CYD dengue vaccine (alone) at D0+28D (M1), M1+6 months (M7), and M1+12 months (M13)

Study Visits

Subjects will have to attend 6 (Group 1) or 8 (Group 2) visits and will have 1 phone call for the 6month follow-up after the last injection of the CYD dengue vaccine. Interim phone calls will be given 7 days after each injection and 2 months after blood samples during the 6-month period after each vaccination.

An unscheduled visit and/or phone call will take place during the study pause in order to communicate the new data on the CYD dengue vaccine to each subject. This visit will be either before or at the time of the next visit initially planned (V05, V06 or V07, depending on study progression). A "Dear Patient Letter" approved by IEC/IRB will be explained to the subjects to share with them the new safety data. Dengue serostatus at baseline may be communicated to the subjects at the time of this unscheduled visit if available.

Subject's participation in the study is expected to be of 18 or 19 months. Time for the approval of Protocol Amendment 1 by the competent authorities and completion of the associated logistic tasks will result into a hold of study activities of several months (approximately 2 months), and thus, to an extension of study duration for dengue exposed subjects.

Blood Samples

Subjects will provide blood samples:

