- 7) Inject the second dose of Gardasil to all subjects (Groups 1 and 2) and the second dose of the CYD dengue vaccine to subjects in Group 1 (6 months post-dose 1).
- 8) Keep the subject under observation for 30 minutes, and record any immediate AE in the source document.
- 9) Record the date of injection(s), the site and side of injection(s) and the route of administration(s), as well as the dose number of the vaccine(s).
- 10) Give the parent/legally acceptable representative a DC.
- 11) Remind the parent/legally acceptable representative to bring back the DC when they return for Visit 5 at a specified date and time.
- 12) Complete the relevant CRF pages for this visit.

Phone Call 4 (PC4) (Month 6 + 7 days; 7 days [+8 days] after Visit 4)

The same procedures as those descried for PC1 will be followed.

Additional Unscheduled Visit 0 and /or Phone call (PC0)- As per Protocol Amendment 1

This unscheduled visit is to take place between Visit 4 and Visit 5 or between Visit 5 and Visit 6 depending on the group and the progression in the study, after approval of the Protocol Amendment 1 by the IEC/IRB. During this visit, subjects will be informed about the increased risk of hospitalized or severe dengue for those unexposed to dengue infection prior to the first injection with the CYD dengue vaccine by the mean of the "Dear Patient Letter", and will be informed about their dengue serostatus at baseline if available

At the latest, this visit will take place at the same time as next scheduled visit.

Visit 5 (Month 7; 28 [+14] days after Visit 4)

The Investigator or designated study personnel will:

For subjects who will return at V05 after the suspension of vaccination

- Present the changes brought to the study design to the subject/subject's parent (s)/legally acceptable representative(s) in more detail, answer any of his/her/their questions, and ensure that he/she/they has/have been informed of all aspects that are relevant to their decision to continue participating in the study
- 2) Have the subject and/or the subject's parent (s)/legally acceptable representative(s), date and sign the new AF and/or ICF version, as applicable

For dengue unexposed or dengue exposed subjects who continue in the study but refuse further CYD dengue vaccine injection:

3) Obtain the blood sample (see Section 7.1 for detailed instructions regarding the handling of blood samples) for HPV immunogenicity assessment post Gardasil Dose 2

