For subjects dengue exposed who continued in the study and agree to receive the remaining CYD dengue vaccine injection(s):

- 4) Review the pages of the DC with the parent/legally acceptable representative, including any AEs, medications, or therapy that occurred since vaccination.
- 5) Perform a physical examination.
- 6) Record the subject's axillary temperature (Group 2).
- 7) Check concomitant medications and record every reportable medication ongoing at the time of vaccination.
- 8) Obtain the blood sample (see Section 7.1 for detailed instructions regarding the handling of blood samples)
- 9) For female subjects of childbearing potential, perform a urine pregnancy test before injection (subjects in Group 2 only).
- 10) Review temporary and definitive contraindications to vaccination (Group 2).
- 11) Inject the second dose of the CYD dengue vaccine to eligible subjects in Group 2 (6 months post-dose 1).
- 12) Keep the subject under observation for 30 minutes, and record any immediate AE in the source document (Group 2).
- 13) Record the date of injection, the site and side of injection and the route of administration, as well as the dose number of the vaccine (Group 2).
- 14) Give the parent/legally acceptable representative a DC for Group 2 and Group 1 (for Group1, the DC is for SAE collection only).
- 15) Remind the parent/legally acceptable representative of subjects in Group 2 to bring back the DC when they return for Visit 6 at a specified date and time.

- 16) Remind the parent/legally acceptable representative of subject in Group 1 to bring back the DC when they return for Visit 7 at a specified date and time.
- 17) Complete the relevant CRF pages for this visit.

Phone Call 5 (PC5) (Month 7 + 7 days; 7 days [+8 days] after Visit 5)

The same procedures as those descried for PC1 will be followed.

Visit 6 (Month 8; 28 [+14] days after Visit 5)

This visit is applicable only for subjects in Group 2 and the same procedures as those described for Visit 3 will be followed with in addition:

For subjects who will return at V06 after the suspension of vaccination

- Present the changes brought to the study design to the subject/subject's parent (s)/legally acceptable representative(s) in more detail, answer any of his/her/their questions, and ensure that he/she/they has/have been informed of all aspects that are relevant to their decision to continue participating in the study

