9.2.2.3 Safety Assessment Methods

At each visit, the Investigator or a delegate will perform a clinical or medically-driven physical examination, and will ask subject or legally acceptable representative about any solicited reactions and unsolicited AEs recorded in the DC or MA, as well as about any other AEs that may have occurred since the previous visit. All relevant data will be transcribed into the CRF according to the instructions provided by the Sponsor.

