##### ***Safety***

All analyses will be descriptive; no hypotheses will be tested. Safety will be assessed for all subjects and for immune subjects after each and any dose of Gardasil and CYD Dengue vaccine. Moreover, a complementary analysis will be performed for each dose of CYD dengue vaccine, for each and any group, on non-immune subjects.

As there are differences in the intensity considered for measurable reactions depending on ages of subjects, a complementary analysis will be performed according to the following age groups: 9-11 years and 12 to 13 years.

For the main parameters, 95% CIs of point estimates will be calculated using the normal approximation for quantitative data and the exact binomial distribution (Clopper-Pearson method, quoted by Newcombe) for single proportions.

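### The amended Visit 5 list asks for diary-card review only from exposed subjects taking more CYD, which contradicts Protocol 9.2.2.3 and puts second-dose safety data from unexposed subjects and refusers at risk

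*Protocol*

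**What the plan says.** At Visit 4 every family receives a diary card and is told to bring it back at Visit 5 (Protocol 5.1.4). After the amendment, Visit 5 has three parts:

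- Steps 1 and 2, for anyone returning at V05 after the pause: explanation of the changes, and consent or assent.
- Step 3, headed "For dengue unexposed or dengue exposed subjects who continue in the study but refuse further CYD dengue vaccine injection". Its single item is "Obtain the blood sample (see Section 7.1 for detailed instructions regarding the handling of blood samples) for HPV immunogenicity assessment post Gardasil Dose 2".
- Steps 4 to 17, headed "For subjects dengue exposed who continued in the study and agree to receive the remaining CYD dengue vaccine injection(s". Step 4 is "Review the pages of the DC with the parent/legally acceptable representative, including any AEs, medications, or therapy that occurred since vaccination". Step 7 is the concomitant-medication check and step 17 is completion of the CRF pages.

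Protocol 5.1.3 says of unexposed subjects: "They will not attend any further study visits, except the unscheduled visit and/or the next schedule visit planned to sign the AF and ICF". The only procedure it then names for that visit, besides signing, is the offer of an HPV sample.

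In the schedule (Protocol Table of Study Procedures, SAP Table 3.1) the V05 to V08 columns, which hold the rows for diary cards checked and collected, are headed as applying to exposed or immune subjects only.

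Protocol 9.2.2.3 is general. Its rule covers every study visit, and under it the investigator or a delegate "will ask subject or legally acceptable representative about any solicited reactions and unsolicited AEs recorded in the DC or MA". It sets no limit by serostatus or by consent to further CYD.

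The SAP (5.1.2.2, Safety) assesses safety after each and any dose of both vaccines in all subjects and in immune subjects, and adds that "a complementary analysis will be performed for each dose of CYD dengue vaccine, for each and any group, on non-immune subjects".

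**The concern.** The step-by-step list is the most specific instruction a site has for this visit, and it was rewritten for this amendment. For subjects not taking more CYD it leaves out the one step that would bring in a card the family already holds. The general rule in 9.2.2.3 points the other way, and nothing says which prevails.

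What is at stake is the solicited and non-serious unsolicited safety record after the second dose. If sites follow the list, that record would be missing according to baseline serostatus and willingness to continue, not at random. Seronegative subjects are the group whose risk prompted the amendment, and the SAP plans a separate by-dose safety description for them. Refusers are exposed subjects, so their cards feed the immune and all-subject safety analyses.

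**Working it through.** The plan gives no figure to reproduce here. The check sets the passages side by side.

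**Step 1. Which card is outstanding at the first visit after the pause** (next visits from Protocol 5.1.3, procedures from 5.1.4):

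| Next visit | Outstanding second-dose card | Diary step listed for unexposed subjects and refusers? |
|---|---|---|
| V05, Group 1 | Gardasil dose 2 + CYD dose 2 | No |
| V05, Group 2 (8 subjects) | Gardasil dose 2 only; CYD dose 2 not yet given | No |
| V06, Group 2 | CYD dose 2 | Yes: Visit 6 repeats Visit 3, which opens with a diary check, with no split |
| V07, both groups | Second-dose card was due earlier, at V05 (Group 1) or V06 (Group 2) | Visit 7 repeats Visit 4, which opens with diary review, with no split |

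The explicit omission is therefore confined to V05. At V06 and V07 the only ambiguity comes from 5.1.3 and the column heading.

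**Step 2. Does the schedule resolve it?** SAP Table 3.1 makes footnoted exceptions to its immune-only heading for three items: the HPV sample, the memory aid for subjects receiving no further CYD, and the 6-month call. The diary rows carry none. The schedule does not settle the conflict, and read strictly it agrees with the Visit 5 list.

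**Step 3. Is there another listed route for the data?** The telephone contacts ask about SAEs, including hospitalized suspected dengue (5.1.4). The 6-month contact captures SAEs and, if applicable, AEs of particular interest (11.1). Under 5.1.3 unexposed subjects have no later scheduled visit. No later listed contact clearly recovers solicited reactions or non-serious unsolicited events.

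**Step 4. What one card holds.** Counting both end days:

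- Injection-site reactions, D0 to D7: 7 − 0 + 1 = 8 days.
- Systemic reactions, D0 to D14: 14 − 0 + 1 = 15 days.
- Unsolicited events, D0 to D28: 28 − 0 + 1 = 29 days.

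**Step 5. What happens in the analysis.** SAP 5.3.1 replaces no missing safety data. SAP 4.4.1.1.3 sets the presence of a reaction to missing when nothing is recorded, unless the investigator recorded its absence. An unread card would become missing data in the by-dose tables.

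**Step 6. How many subjects.** For Group 2 at V05 the documents give 8, without serostatus. For Group 1 at V05 they give no number. They do not say how many of either are unexposed or refuse.

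**The case against.** The strongest reply is that retrieval is already required. Section 9.2.2.3 covers every visit and every subject. Section 11.1 has the investigator interview families to collect what the card records. Visit 4 tells every family to bring the card to Visit 5, and the call after Visit 4 reminds them to complete it and allows a follow-up visit. Sites also work from CRF completion and operating guidelines that are not available here. This stands as far as it goes: a reader might infer from the Visit 5 list that the cards were not collected, and the documents do not support that. They support a conflict between instructions.

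The column heading is also not a literal exclusion, since the same columns carry the memory aid and the HPV sample for subjects not taking more CYD. That stands too, but those two items have footnotes and the diary rows do not, so the heading still fails to settle the matter.

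Third, the number is probably small. With 1:1 allocation, the same Visit 4 timing, and V05 about a month later in both groups, Group 1 may have had about as many V05 visits pending as Group 2: 8 of 264, or 3.0%. That is a reasonable assumption but not a documented count. The 8 Group 2 subjects had no CYD dose 2 to report, so their cards bear only on the Gardasil analyses.

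Finally, a reader might infer that families refuse because of a reaction, which would bias the retained data. No passage links the two. The disclosure that precedes the decision concerns serostatus-related risk, and SAEs are collected throughout in any case.

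**Conclusion.** The Visit 5 list is wrong as written because it conflicts with Protocol 9.2.2.3. Followed literally, unexposed subjects and refusers returning at V05 after the pause would not have an outstanding second-dose card reviewed, although the SAP reports safety after each dose and, for CYD, separately in non-immune subjects.

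The size cannot be stated beyond this: up to one full second-dose diary record per affected subject, for an unreported number of Group 1 subjects and for whichever of the 8 Group 2 subjects are unexposed or refuse (Gardasil card only). This rests on a literal reading of the list.

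Two wider readings are tempting and fail. One is that second-dose diaries are lost at whichever visit comes first after the pause; the Visit 6 and Visit 7 texts already include a diary check without a split. The other is that the seronegative stratum loses all or a large share of its second-dose safety data; the documents give no count to support any percentage, and cards due before the pause are not touched.

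The correction is still worth making: it costs almost nothing and decides whether data already in families' hands are collected.

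**What to change.** 1. In Protocol 5.1.4, Visit 5, move step 4 (diary, AE and medication review), collection of the card, and step 17 (CRF completion) above the split, so that they apply to every subject attending.
2. In Protocol 5.1.3, add return and review of any outstanding diary card to the unexposed subject's consent visit. This also removes the ambiguity at V06 and V07.
3. In the Table of Study Procedures and SAP Table 3.1, footnote the rows for diary cards checked and collected as applying to all attending subjects.

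The cost is wording and a few minutes at a visit the subject already attends, with no extra visit or sample. The SAP describes the amendment's changes in the past tense, so these visits may already be over. If so, what remains useful is for the SAP to report how many second-dose diary cards were available, by group and baseline dengue status, beside the by-dose safety tables.
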